9.5 Pregnancy

If a study subject becomes pregnant during participation in this clinical study, site staff must notify the sponsor within 24 hours of learning of the pregnancy by completing the Pregnancy Report Form and either faxing or emailing this form to [REDACTED]

[REDACTED] Subjects who

become pregnant during the trial will be withdrawn from active participation in the trial and will discontinue study drug after an appropriate period of down-titration.

United Therapeutics Global Drug Safety will follow up with the Investigator each trimester to ensure appropriate data are provided regarding the outcome of the pregnancy, and to ask the Investigator to update the Pregnancy Report Form. Pregnancy only becomes an AE / SAE if there is an abnormal outcome, a spontaneous abortion, a termination for medical reasons other than PAH, or a congenital anomaly in the offspring.

10 DATA MANGEMENT AND STATISTICS

Completed CRFs will be forwarded to United Therapeutics or its designee for processing. A quality-assured computerized database will be constructed. Data will be listed and also will be summarized either in tabular and/or graphical presentations.

The safety of UT-15C SR will be assessed using laboratory assessments and reports of adverse events. All reported adverse events will be assigned MedDRA terms which will be listed and summarized according to intensity, seriousness and causality.

Efficacy assessments (6-Minute Walk/Borg Dyspnea Score) may be compared to assessments in Protocols TDE-PH-202, TDE-PH-203, TDE-PH-205, TDE-PH-301, TDE-PH-302, TDE-PH-308, or TDE-PH-304, as appropriate. Doses of UT-15C SR will be listed, summarized and analyzed for trends over time.

11 PACKAGING AND FORMULATION

11.1 Study Drug Content

United Therapeutics will supply UT-15C SR for administration in the study. UT-15C SR tablets will be provided as 0.25, 0.5, 1, and 2.5 mg strengths and may also be provided as a 0.125 mg strength, if available. UT-15C SR 0.125 mg (blue), 0.25 mg (green), 0.5 mg (white), 1 mg (yellow), and 2.5 mg (pink) tablets will be provided in child resistant bottles each containing 100 tablets, or in other appropriate packaging configurations as may be required as more experience with long-term dosing requirements is obtained.

11.2 Study Drug Labeling

Each bottle and/or other packaging (e.g., kits/cartons) for UT-15C SR will be labeled with at least the following information: study drug, strength, quantity, manufacture date, lot number, sponsor name and address, and storage conditions.

11.3 Study Drug Storage and Handling

All study drug will be stored in accordance with label specified storage conditions. UT-15C SR should not be frozen or exposed to heat.

Subjects should be instructed to return all study drug, including empty bottles or other containers, to the appropriate study personnel for drug accountability and compliance assessments, as appropriate.

11.4 Study Drug Supply and Return

Study sites will be supplied with a sufficient quantity of UT-15C SR to begin enrollment in the study. Appropriate arrangements will be made for resupply with respect to each subject's visit schedule. All unused study drug dispensed to the subject should be returned to the study site (including empty and unopened bottles).

11.5 Study Drug Accountability

The Investigator is responsible for study drug accountability and reconciliation overall and on a per subject basis. Drug accountability records are to be maintained during the study and these records include: the amount of study drug received from the Sponsor, the amount dispensed to each subject, and the amount of unused drug. At each visit, site personnel should assess drug dispensed, drug returned, and dosing information to confirm drug accountability and compliance. Once a representative from the Sponsor is able to confirm drug accountability for that subject, study drug will be returned to a Sponsor designated location for destruction.

12 REGULATORY AND ETHICAL OBLIGATION

12.1 Regulatory Requirements

The study will be conducted in accordance with ICH and GCP guidelines and all applicable national regulations. The Sponsor will obtain the required approval from each national regulatory authority to conduct the study. During the conduct of the study an annual safety report will be compiled by the Sponsor for submission to those regulatory authorities and IRBs/ECs that require it. Any additional national reporting requirements as specified by the applicable regulations, regulatory authorities, or IRB/EC will also be fulfilled during the conduct of the study.

12.2 Informed Consent Requirements

Before a subject is enrolled in the study, the Investigator or his/her designees must explain the purpose and nature of the study, including potential benefits and risks and all study procedures to the subject. The subject must sign and date an IRB/EC-approved informed consent form prior to the conduct of any study-related activities. A copy of the signed consent form will be given to the subject and the original will be retained in the study site's records.

12.3 Institutional Review Board/Independent Ethics Committee Approval

Prior to study initiation at each site, the Investigator will obtain approval for the study from an appropriate IRB/EC and provide the Sponsor with a copy of the approval letter. The IRB/EC must also review and approve the study site's informed consent form and any other written information provided to the subject prior to enrollment, as well as any advertising materials used for subject recruitment. Copies of the informed consent form and advertising materials must be forwarded to the Sponsor for review before submission to the IRB/EC prior to the start of the study.

If, during the study, it is necessary to amend either the protocol or the informed consent form, the Investigator is responsible for obtaining IRB/EC approval of these amended documents prior to implementation. Copies of the IRB/EC correspondence and approval letters must be sent to the Sponsor.

During the conduct of the study, an annual progress report will be compiled by the Sponsor for submission to those IRBs/ECs that require it.

A written summary of the study will be provided by the Investigator to the IRB/EC following study completion or termination according to the IRB or EC standard procedures. Additional updates will also be provided in accordance with the IRB/EC's standard procedures.

12.4 Prestudy Documentation Requirements

Before the commencement of the clinical trial, the following documents will be provided to the site: Investigator's Brochure, Protocol, Informed Consent Form, Budget Agreement, and Case Report Form.

The site will be required to provide the following documents to United Therapeutics Corporation or designee prior to study start: Signature page of the protocol, Form FDA 1572, IRB/EC Composition and

Roster, IRB/EC approval letters for protocol and informed consent, and Curriculum Vitae of study staff listed on the 1572.

12.5 Subject Confidentiality

Every effort will be made to keep medical information confidential. United Therapeutics Corporation, the FDA or other regulatory bodies, and the IRB/EC governing this study may inspect the medical records of any subject involved in this study. The Investigator may release the subject's medical records to employees or agents of the Sponsor, the IRB/EC or the FDA or appropriate local regulatory agencies for purposes of checking the accuracy of the data. A number will be assigned to all subjects and any report published will not identify the subject's name.

12.6 Reporting of Clinical Trial Results

The timely communication of scientifically valid results, positive and negative, from this clinical trial will occur. Avenues for such public communications may include the following: peer-reviewed publications of original research and scientific, nonpromotional summaries on a publicly accessible registry (i.e., a Web site). A committee of principal investigators participating in the clinical trial and enrolling the highest number of subjects will oversee the publication of study results.

The guidelines such as the Good Publication Practice (GPP) guidelines for pharmaceutical companies (gpp-guidelines.org), and guidelines sponsored by the International Committee of Medical Journal Editors and the Pharmaceutical Manufacturers Association (PhRMA) will be endorsed. In addition, an attempt will be made to fulfill any country specific regulatory requirements for publication of clinical trials conducted within that country.

13 ADMINISTRATIVE AND LEGAL OBLIGATIONS

13.1 Protocol Amendments and Study Termination

Protocol amendments that could potentially adversely affect the safety of participating subjects or that alter the scope of the investigation, the scientific quality of the study, the experimental design, dosages, duration of therapy, assessment variables, the number of subjects treated, or subject selection criteria may be made only after consultation between United Therapeutics Corporation or its designee and the Investigator.

All protocol amendments must be submitted to and approved by the appropriate regulatory authorities and IRB/Ethics Committee prior to implementation.

A report documenting study termination must also be submitted to and acknowledged by the appropriate IRB/EC for each study site.

At the end of the study, where applicable, a final report will be provided to the local regulatory agencies.

13.2 Study Documentation and Storage

In accordance with federal/national regulations, ICH, and GCP guidelines, the Investigator must retain study records for at least 2 years after the last approval of a marketing application in an ICH region and until there are no pending or contemplated marketing applications in an ICH region or at least 2 years have elapsed since the formal discontinuation of clinical development of the investigational product. For investigators in the European Economic Area (EEA), the study records should be maintained for at least 15 years after study discontinuation. The Investigator must notify United Therapeutics Corporation before any disposal or change in location of study records.

13.3 Study Monitoring and Data Collection

In accordance with federal/national regulations, ICH, and GCP guidelines, monitors for United Therapeutics Corporation or its designee will periodically contact the site and conduct on-site visits. During these visits, the monitor will at a minimum: confirm ethical treatment of subjects, assess study progress, review data collected, conduct source document verification, verify drug accountability periodically, and identify any issues requiring resolution.

The Investigator agrees to allow the monitor direct access to all relevant documents and to allocate his/her time and his/her staff to the monitor to discuss any findings or any relevant issues.

**ABBREVIATIONS AND DEFINITIONS**

Abbreviation	Definition
6MWD	Six minute walk distance
AE	Adverse event
BID	Twice daily
CRF	Case report form
CSR	Clinical study report
ERA	Endothelin receptor antagonist
K-M	Kaplan-Meier
MedDRA	Medical Dictionary for Regulatory Activities
OL	Open-label
PAH	Pulmonary arterial hypertension
PDE-5i	Phosphodiesterase type 5 inhibitor
PT	Preferred term
SAP	Statistical Analysis Plan
SOC	System organ class
SR	Sustained release
TID	Three times daily
WHO	World Health Organization

## 1 PREFACE

This statistical analysis plan (SAP) provides further details of the planned analyses for the TDE-PH-304 study. The purpose of this SAP is to ensure that the statistical methodologies that will be used, and the data listings, summary tables, and figures which will be produced, are appropriate and complete to support valid conclusions regarding the study objectives and the completion of the Clinical Study Report (CSR). Additional post-hoc or unplanned analyses, which are not defined in this SAP, may be performed to support the clinical development program. Such analyses will be documented in the CSR.

## 2 STUDY OBJECTIVES AND ENDPOINTS

### 2.1 OBJECTIVES

The objectives of this study are to:

- Provide, or continue to provide, UT-15C sustained release (SR) for eligible subjects who participated in protocols TDE-PH-202, TDE-PH-203, TDE-PH-205, TDE-PH-301, TDE-PH-302, TDE-PH-308, or additional UT-15C SR clinical protocols.
- Assess the long-term safety of UT-15C SR in these subjects through assessment of adverse events and laboratory parameters.
- Assess the effect of continued therapy with UT-15C SR on exercise capacity after one year of treatment.

### 2.2 ENDPOINTS

The safety endpoints are as follows:

- Adverse events (AEs)
- Clinical laboratory parameters

Pulmonary arterial hypertension (PAH) concomitant medications also will be documented.

Efficacy will be assessed by a 6-Minute Walk Test and Borg Dyspnea Score to be conducted after each subject has completed one year of therapy with UT-15C SR.

## 3 STUDY DESIGN

This is an open-label (OL) study. Each subject's visit schedule will allow assessments after defined periods of exposure to UT-15C SR (3, 6, 12, 24, and 36 months total exposure). The study will continue with yearly visits beyond 36 months until either UT-15C SR is approved by the appropriate regulatory authorities or the study is discontinued by the sponsor. Therefore, the actual date of each visit will be determined by the date on which the subject first received UT-15C SR (e.g., the date of study drug initiation in TDE-PH-301, TDE-PH-302, or TDE-PH-308 for subjects who were randomized to active therapy in those studies, and the date of UT-15C SR initiation in this study for subjects who were randomized to placebo in the previous controlled study). Note that the TDE-PH-202, TDE-PH-203, and

TDE-PH-205 studies are OL in design and therefore will follow the regimen for subjects receiving UT-15C SR.

Subjects enrolled from the TDE-PH-202 study who were in Dose Groups 1 or 2 and permanently discontinued treatment may enter the study if they undergo all premature termination assessments prior to discontinuing study drug and complete all remaining scheduled study visits and assessments (with the exception of the hemodynamic measurements) through Week 12. These subjects should follow the same procedures as subjects who received placebo in the previous study and will begin on a dose of 0.25mg twice daily (BID).

Subjects randomized to UT-15C SR in Protocol TDE-PH-301, TDE-PH-302, or TDE-PH-308 will complete visits 2-5 and yearly visits thereafter, while subjects randomized to placebo in Protocol TDE-PH-301, TDE-PH-302, or TDE-PH-308 will complete visits 1-5 and yearly visits thereafter. A 6-Minute Walk Test and Borg Dyspnea Score will be conducted at the visit occurring 12 months after the subject's initial exposure to UT-15C SR.

Monthly telephone calls must be conducted for all subjects actively participating in TDE-PH-304, regardless of study drug allocation in the previous study. In addition to the scheduled study visits, all subjects must be seen in the clinic no less than once every six months for routine standard of care medical evaluation.

#### **4 RANDOMIZATION**

This study is not randomized. All subjects will receive UT-15C SR during the OL study.

#### **5 SEQUENCE OF PLANNED ANALYSES**

Interim analyses will occur to support regulatory submissions (e.g., NDA, 120-day safety updates, etc.) and as frequently as yearly in order to continuously monitor the long-term safety of oral treprostinil in this ongoing study. For each interim analysis, the data currently in the database will be soft locked by Data Management and provided to Statistics and Programming for creation of output as described in this analysis plan.

#### **6 SAMPLE SIZE CONSIDERATIONS**

The sample size for this study was not derived through a power calculation, but rather an assumption about the number of subjects who would enroll in this OL study after completion of their UT-15C SR clinical protocol. The sample size is expected to be approximately 900 subjects from protocols TDE-PH-202, TDE-PH-203, TDE-PH-205, TDE-PH-301, TDE-PH-302, and TDE-PH-308, plus additional subjects from any additional UT-15C SR clinical protocols evaluating subjects with PAH.

#### **7 ANALYSIS POPULATIONS**

All available data from all subjects enrolled in the TDE-PH-304 study will be used as detailed in this analysis plan. Additionally, subjects who were treated with active drug during the parent study and who enrolled in the TDE-PH-304 study will have the data from the parent study included in the data analyses and listings for this study, as detailed in this SAP.

Subjects who were treated with placebo during the parent study and who enrolled in the TDE-PH-304 study will have baseline data only from the parent study included in the data analyses and listings for this study, as detailed in this SAP.

## **8 GENERAL CONSIDERATIONS FOR DATA ANALYSES**

All available data for subjects enrolled in TDE-PH-304 (regardless of treatment with active drug) will be included in each soft lock and will be listed. All available data for enrolled subjects who were treated with active drug in study TDE-PH-304 will be summarized, as detailed in this SAP. Subjects from the 200 series studies (TDE-PH-202, TDE-PH-203, and TDE-PH-205) that enrolled into the TDE-PH-304 study will be pooled for summarization purposes with the two de novo subjects previously enrolled in the TDE-PH-301 study. These two de novo subjects were initially enrolled in TDE-PH-301, but were later withdrawn from that study following a temporary drug recall in June 2006 and were subsequently directly enrolled in the TDE-PH-304 OL study. Likewise, subjects from studies TDE-PH-301 and TDE-PH-308 will be pooled for summarization purposes.

In general, listings will be sorted by subject number and scheduled assessment (if applicable). Listings will include assessment date, assessment time (if available), and study day. For data collected on a fixed schedule, the assessment identifier will also be included on the listing.

In general, the data will be summarized by scheduled assessment (if applicable). For continuous variables, the summary statistics will include the mean, standard deviation, standard error, median, lower quartile, upper quartile, minimum, and maximum. Minimums and maximums will be expressed using the level of precision in which the variable was collected. All other statistics will be rounded, using an additional decimal point. For discrete variables, summaries will include the frequency and percent in each category. Percentages will be rounded to a whole number. Whenever practical, categories of discrete variables will be ordered and labeled as they appear in the case report form (CRF), and all categories represented on the CRF will be included in summaries, even when they do not apply to any subjects in the study.

### **8.1 EXAMINATION OF SUBGROUPS**

All summaries will be provided by previous study and overall to allow examination of impact from previous study. Other exploratory subgroup analyses will be performed as data permit.

### **8.2 PREMATURE DISCONTINUATION AND MISSING DATA**

A subject may voluntarily withdraw or be withdrawn from the study by the Investigator at any time for reasons including, but not limited to, the following:

- The subject wishes to withdraw from further participation.
- A serious or life-threatening AE occurs or the Investigator considers that it is necessary to discontinue study drug to protect the safety of the subject.
- The subject deviated from the protocol.
- The subject's behavior is likely to undermine the validity of his/her results.
- The subject becomes pregnant

### 8.3 MULTIPLE COMPARISONS AND MULTIPLICITY

No multiple comparison adjustments are planned for analysis of this study.

## 9 STUDY POPULATION

### 9.1 SUBJECT ACCOUNTABILITY

A listing of subject disposition and study drug exposure will include subject number, previous study number, first and last active drug dose dates, data cutoff date, study drug exposure (weeks), discontinuation status, reason for discontinuation, and any details regarding discontinuation status. Study drug exposure will account for all active drug exposure, including time on active drug during the parent study, where applicable. A comprehensive listing will be generated containing subject number and previous study number. The summary of subject accountability will include the number (percent) of subjects in each double-blind study treatment group, who consented prior to study assessments, who discontinued the study prematurely, who reached each visit as their maximum visit, and each reason for discontinuation. These summaries will be provided by previous study and overall.

### 9.2 ELIGIBILITY CRITERIA

The listing of admission criteria will include each subject's status regarding meeting all admission criteria for the TDE-PH-304 study as well as any details noted in the CRF. The listing of admission criteria violations will include only those subjects who did not meet all admission criteria and any details regarding their criteria evaluation. The summary of admission criteria violations will include a categorical summary of the CRF question "Did the subject meet all entry criteria," with possible choices of no, yes, and missing, by previous study and overall.

### 9.3 OTHER DESCRIPTIONS OF STUDY POPULATION

#### 9.3.1 *Demographics*

The listing of subject demographics will include subject, previous study number, age (years), sex, ethnicity, and race. Age is calculated as the age at the time of the first dose of active drug (active drug dosing occurred either during the parent study or during the OL study, depending on whether subjects were treated with active or placebo in the parent study, respectively). The summary of demographics will include descriptive statistics for age (years) and categorical summaries for age (<18, 18-64, >64 years), sex, ethnicity, and race. Each categorical summary will include a row for missing, as applicable, in order to sum to 100% of subjects. These summaries will be provide by previous study and overall.

#### 9.3.2 *PAH History*

The listing of PAH history will include the number of years since PAH diagnosis, etiology, WHO functional class at baseline, background PAH therapy (none, endothelin receptor antagonist [ERA], phosphodiesterase type 5 inhibitor [PDE-5i], and ERA+PDE-5i), background ERA, and background PDE-5i. The number of years since PAH diagnosis is calculated as the time from diagnosis to first dose of active drug. The summary of PAH history will include descriptive statistics for years since PAH diagnosis, six minute walk

distance at baseline, and Borg Dyspnea Score at baseline. The summary will also include categorical summaries for etiology, background PAH therapy, background ERA, background PDE-5i, and WHO functional class at baseline.

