1.2 Treprostinil Background

1.2.1 UT-15C SR Nonclinical

UT-15C is a novel salt form of Remodulin[®] (treprostinil) Injection and Tyvaso[®] (treprostinil) Inhalation Solution, which are approved in the United States and other countries for the treatment of patients with PAH. The active pharmaceutical ingredient, treprostinil, exists as the sodium salt in the drug product of Remodulin and Tyvaso. Given that the only change to the drug substance synthesis route for UT-15C is the diethanolamine addition step, and treprostinil is not altered, the bioactive form of treprostinil diethanolamine and treprostinil sodium is predicted to be identical. Therefore, in addition to the nonclinical studies conducted with UT-15C, an extensive amount of pharmacology, pharmacokinetic, and toxicology information on treprostinil sodium is available from Remodulin and Tyvaso development. During the development of Remodulin, treprostinil sodium was administered SC and / or IV in acute toxicity studies, repeat-dose toxicity studies, reproductive toxicity studies, and genotoxicity studies, and has a well defined clinical safety profile. Treprostinil sodium was administered via continuous infusion to both rats and dogs in toxicity studies for up to 6-months, which supported the chronic administration of Remodulin to patients.

In addition to the extensive toxicology data with treprostinil sodium, the toxicity and toxicokinetic profiles of UT-15C have been evaluated in acute and repeat dose oral toxicity studies of up to 13 weeks in duration in rodents and up to 9 months duration in dogs. UT-15C has also been evaluated in reproductive-developmental toxicity studies in pregnant rats and rabbits and in an *in vivo* rat micronucleus assay.

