3.3.2.3. Concomitant Medications

In this open-label study, there are no restrictions on concomitant medications, with the exception of the addition of prostanoid therapy. If chronic parenteral prostanoid therapy is added for the treatment of worsening PAH, the subject will be discontinued from the study. Short term, parenteral prostanoid therapy may be initiated if required (e.g., the patient is temporarily unable to take oral medications). If prostanoid therapy is initiated for any other reason than worsening PAH, eligibility for continued participation in this study will need to be reviewed by the Medical Monitor on a case by case basis. For subjects enrolling into TDE-PH-304 from the TDE-PH-203 study continued chronic use of inhaled treprostinil (Tyvaso®) is acceptable.

ERAs and PDE-5 inhibitors may be added or withdrawn at any time. Concomitant PDE-5 inhibitors, ERAs, and other medications related to the subject's treatment will be collected at each study visit and recorded in the CRF.

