## 10.2 CLINICAL EVENTS

Clinical events, including death, study discontinuation for any reason, addition of PAH therapy, and addition of parenteral PAH therapy, will be listed, including date of each event, if applicable, as well as the subject's previous background therapy status (naïve, single background therapy, or double background therapy). Note that events may have occurred during the parent study for those subjects treated with active drug during the parent study, thus event data from the parent study will be included in these data analyses. The following combinations of clinical events will be utilized for summarization and plotting purposes, separately:

- Study discontinuation for any reason
- Death or discontinuation due to disease progression
- Death, discontinuation due to disease progression or addition of PAH therapy
- Death, discontinuation due to disease progression or addition of parenteral PAH therapy
- Death

Summary tables will be produced by previous study and overall and will display the number (percent) of subjects who experienced each event combination detailed above. Kaplan-Meier (K-M) curves for the above combinations of clinical events will be provided separately. Each K-M plot will include a time to clinical event curve for each of the previous studies overlaid on the same plot.

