## 11 SAFETY ANALYSES

### 11.1 EXTENT OF EXPOSURE

Study drug exposure will be listed, including subject number, previous study, concomitant medication use, BID to three times daily (TID) transition, exposure (weeks), and categorical exposure (by visit). Exposure is calculated as the time exposed to active study drug. For subjects treated with active drug during the parent study, exposure calculations will include their exposure during the parent study. For subjects treated with placebo during the parent study, exposure calculations will include only the exposure to active drug during the OL study. The summary of disposition and study drug exposure will detail the number (percent) of subjects who died during the study, as well as the study drug exposure both by categorical visits ( $\geq 3$  months,  $\geq 6$  months, etc.) and using descriptive statistics. The total study drug exposure (pt-years) will also be displayed.

Study drug dosing will be summarized at each visit by previous study and overall. The summary will include a categorical summary of current status (in study, death, progression of PAH, AE, consent withdrawn, lost to follow-up, discontinued for other reasons, etc.) and study drug dose (<1 mg, 1-<2.5 mg, 2.5-<5 mg, 5-<10 mg, 10-<20 mg, 20-<30 mg BID/TID), as well as a descriptive statistics summary of study drug dose (mg BID/TID).

Study drug dosing will also be summarized at each visit by PAH background medication use, grouping subjects into monotherapy and combination therapy groups. The summary table will mimic that presented in the summary of study drug dosing by previous study, but will produce a separate summary table for each PAH background medication use group.

The summary of BID to TID transition will detail the number (percent) of subjects who completed this transition and who had to transition back to BID (if applicable), and descriptive statistics on the doses both before and after the transition by previous study and overall. All of these summaries will be provided by previous study and overall.

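### SAP 9.3.2 has no background-therapy level for the inhaled treprostinil that TDE-PH-203 entrants may continue, so it counts each such subject one drug too low

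*SAP*

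**What the plan says.** SAP 9.3.2 lists "background PAH therapy (none, endothelin receptor antagonist [ERA], phosphodiesterase type 5 inhibitor [PDE-5i], and ERA+PDE-5i", and the matching table uses the same variable: "The summary will also include categorical summaries for etiology, background PAH therapy, background ERA, background PDE-5i, and WHO functional class at baseline". There is no prostacyclin level and no level for other drugs.

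Protocol 3.3.2.3 makes an explicit allowance: "For subjects enrolling into TDE-PH-304 from the TDE-PH-203 study continued chronic use of inhaled treprostinil (Tyvaso®) is acceptable". Protocol 1.1 includes inhaled treprostinil among the approved PAH drugs. Protocol 1.2.1 says of Remodulin and Tyvaso, "which are approved in the United States and other countries for the treatment of patients with PAH".

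Two later SAP sections group subjects by background treatment in different terms. Section 10.2 lists with each clinical event "the subject's previous background therapy status (naïve, single background therapy, or double background therapy". Section 11.1 summarises dosing "by PAH background medication use, grouping subjects into monotherapy and combination therapy groups" (Table 14.1.6.2). Neither section names the drugs that count, and neither refers to 9.3.2.

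SAP 9.3.3 does recognise a combined oral or inhaled prostacyclin class, but only for PAH drugs added during TDE-PH-304. Drugs already in use at entry are reported there by medication name.

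**The concern.** A drug that the protocol permits and describes as PAH therapy has no place in the SAP's only explicit classification of background PAH therapy. The plan counts inhaled prostacyclin as a PAH class if it is started during the extension, but not if the subject arrives on it. It gives no reason for the difference.

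The baseline description of the population is at stake and, depending on how two undefined terms are read, so is one dosing table. Protocol 1.4 says the study will inform long-term dosing patterns, and Protocol 10 promises a look at doses over time. Protocol 1.2.2 states that the circulating active form is the same whichever salt is given. A subject on both oral and inhaled treprostinil is therefore receiving one active moiety by two routes. A dosing summary that placed such a subject with people on oral treprostinil alone would mix two different exposures.

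**Working it through.** The plan states no figure to reproduce and has no power calculation (SAP 6), so the check is a mapping of categories. A subject on chronic inhaled treprostinil can be in one of four states with respect to ERA and PDE-5i. For each state, shortfall = background drugs taken − drugs counted under 9.3.2.

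| Background drugs taken | Level under 9.3.2 | Taken − counted | 10.2 if it follows 9.3.2 | 10.2 if inhaled drug counts |
|---|---|---|---|---|
| Inhaled only | none | 1 − 0 = 1 | naïve | single |
| ERA + inhaled | ERA | 2 − 1 = 1 | single | double |
| PDE-5i + inhaled | PDE-5i | 2 − 1 = 1 | single | double |
| ERA + PDE-5i + inhaled | ERA+PDE-5i | 3 − 2 = 1 | double | no level |

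1. **SAP 9.3.2.** The shortfall is one drug in all four states. This follows from the definition and needs no assumption about how common each state is. The level *none* arises only in the first row.

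2. **SAP 10.2.** The scale is "previous background therapy status (naïve, single background therapy, or double background therapy". If it follows 9.3.2, every row is one level too low. If it counts inhaled treprostinil, the first three rows are placed correctly and the fourth cannot be placed, because the scale stops at two drugs. Both readings leave a gap.

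3. **SAP 11.1.** The instruction is "grouping subjects into monotherapy and combination therapy groups", and the effect depends on what monotherapy means.
   - If it means UT-15C SR alone, leaving out the inhaled drug misplaces only the first row. The other three rows are combination therapy either way.
   - If it means one background drug, rows two and three would fall under monotherapy instead of combination. The first row would have no counted drug and so no group. The fourth is combination either way.

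4. **Possible correction elsewhere.** Under 9.3.3, inhaled treprostinil in use at entry appears by name in Table 14.1.7.1 and Listing 16.2.4.6. The SAP does not say that either feeds the background groupings. SAP 8 pools TDE-PH-203 with TDE-PH-202, TDE-PH-205 and two de novo subjects, so the summary tables have no TDE-PH-203 column from which a reader could make the correction.

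5. **Reach.** The clinical-event summary table and Kaplan-Meier plots are by previous study. The 6MWD and Borg groupings named in SAP 10.1 do not use baseline background therapy.

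**The case against.** The strongest reply is that only one variable is shown to be deficient, and that the information is not lost. Inhaled treprostinil is reported by name, and the listing identifies each user and the parent study. Section 11.1 speaks of background medication use, not of the 9.3.2 variable, so its grouping might be built from the concomitant-medication data. In 10.2 the background status is only a column in a listing. The study is descriptive, and the number of subjects concerned is unknown and may be small.

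Most of this stands, and it limits the point. It does not remove it: reporting a drug by name in one table does not correct a classification in another, and 9.3.2 gives a closed set of levels that omits a permitted drug.

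Two stronger readings are tempting and should be resisted.
- A reader might infer that some subjects *are* shown as naïve or as having no background therapy. That requires a TDE-PH-203 subject on inhaled treprostinil with neither an ERA nor a PDE-5i. The documents give neither that study's background-therapy requirements nor its subjects' medication, so this is possible but not shown.
- A reader might infer that the dosing table and the event listing are wrong. That requires 10.2 and 11.1 to use the 9.3.2 definition, which they do not say. What can be shown there is that a term is undefined.

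**Conclusion.** The point holds for SAP 9.3.2 without further assumption: each TDE-PH-203 entrant continuing inhaled treprostinil is counted exactly one background drug too low in Table 14.1.4 and the PAH history listing. For 10.2 and 11.1 it holds conditionally. The undercount reaches the clinical-events listing if the 9.3.2 definition is carried over, and its effect on Table 14.1.6.2 also depends on the meaning given to monotherapy.

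The number of subjects cannot be stated, because the documents do not say how many TDE-PH-203 entrants use the inhaled drug. Nor do they contain data showing that dose, tolerability or events differ in these subjects; the shared active moiety is a reason to keep them distinguishable, not evidence of a difference. No efficacy summary or time-to-event curve is affected. This is a classification rule that should be corrected because the correction is cheap, but its consequence is confined to descriptive outputs.

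**What to change.** - **SAP 9.3.2:** add an inhaled prostacyclin level, alone and with an ERA, a PDE-5i or both.
- **SAP 10.2:** state that background status is the count of all chronic PAH drugs, inhaled treprostinil included, and add a triple level.
- **SAP 11.1:** use the same count, define monotherapy and combination, and place subjects taking inhaled treprostinil with UT-15C SR under combination therapy in Table 14.1.6.2.
- **Reference time:** use the parent-study medication record at first active dose. If that record is not available, use the 9.3.3 flag for drugs already in use when TDE-PH-304 began, and say so in a footnote.

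The cost is SAP wording and a derived-variable change. PAH medications are already recorded at each TDE-PH-304 visit (Protocol 3.3.2.3), and SAP 7 brings in parent-study data for subjects who received active drug there. Whether those data hold medication use at first active dose cannot be seen from the documents, hence the fallback. The downside is a few sparsely filled categories.
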